13.12.8. Safety Figures

Safety: Figures					
No.	Population	GSK Standard / Example Shell	Title	Programming Notes	Deliverable
Adverse Events					
3.1.	Safety	201584/primary_07/F3.14	Plot of Incidence of Study Drug Injection Site Reaction Adverse Events by Implementation Arm and Visit (Overall and Common) – CAB and/or RPV	Sort by CAB+RPV, CAB, then RPV ISR onset assigned to most recent IM injection Visit	M12, EOS
CCI					
Laboratory					
3.3.	Safety	LIVER14	Scatter Plot of Maximum vs. Baseline for ALT	GSK Statistical Display Standard	M12, EOS
3.4.	Safety	LIVER9	Scatter Plot of Maximum Total Bilirubin vs Maximum ALT – eDISH Plot	GSK Statistical Display Standard	M12, EOS

13.12.9. Other Tables

Study Visit Length					
No.	Population	GSK Standard / Example Shell	Title	Programming Notes	Deliverable
4.1	Safety	OTR T1	Summary of Study Visit Length (minutes) by Visit, Country, and Site (Intervention Phase)	Include overall summary for each visit and country.	IA1, IA2, HL, M12
4.2	Safety	OTR T2	Summary of Study Visit Length (minutes) by Visit and Subgroup (Intervention Phase)	Include all subgroups listed in Section 5.4.2 except for Site & Country	M12
4.3	Safety	NS1	Summary of Remote & Nursing Visits by Visit, Country, and Site	Include overall summary for each visit and country. Add footnote: "All remote visits were recorded in response to missed visits due to Covid-19."	IA2, M12, EOS
4.4	Safety	NS1	Summary of Remote & Nursing Visits by Visit and Subgroup	Include all subgroups listed in Section 5.4.2 except for Site & Country Add footnote: "All remote visits were recorded in response to missed visits due to Covid-19."	M12, EOS

13.12.10. ICH Listings

ICH: Listings					
No.	Population	GSK Standard / Example Shell	Title	Programming Notes	Deliverable
Subject Disposition					
1.	Enrolled	ES2	Listing of Reasons for Study Withdrawal	ICH E3 Add column for Phase, Visit, and Implementation arm	M12, EOS
2.	Enrolled	SD2	Listing of Reasons for Study Treatment Discontinuation	ICH E3 Add column for Phase, Visit, and Implementation arm	HL, M12, EOS
Protocol Deviations					
3.	Enrolled	DV2	Listing of Important Protocol Deviations	ICH E3 Add column for Phase, Visit, and Implementation arm Add a column on the right for "COVID-19 Related". The possible values in this column are Y and N, where Y indicates the deviation is COVID-19 related and N indicates the deviation is non-COVID-19 related.	IA1, IA2, M12, EOS
4.	Enrolled	DV2	Listing of Protocol Deviations Related to COVID-19	Add column for Phase, Visit, and Implementation arm	HL, M12, EOS
5.	Enrolled	DV2	Listing of Implementation Science Protocol Deviations	Add column for Phase, Visit, and Implementation arm	HL, M12, EOS
6.	Safety	IE3	Listing of Subjects with Inclusion/Exclusion Criteria Deviations	ICH E3	M12
Populations Analysed					
7.	Enrolled	SP3	Listing of Subjects Excluded from Safety Population	ICH E3	M12

CONFIDENTIAL

213199

ICH: Listings					
No.	Population	GSK Standard / Example Shell	Title	Programming Notes	Deliverable
Demographic and Baseline Characteristics					
8.	Safety	DM2	Listing of Demographic Characteristics	ICH E3	M12
9.	Safety	DM9	Listing of Race	ICH E3	M12
Efficacy					
10.	Safety	SNAPSHOT11	Listing of Qualitative and Quantitative Plasma HIV-1 RNA Data		HL, M12
11.	Safety	SNAPSHOT12	Listing of Study Outcome (50 copies/mL cutoff) at Month 12 – Snapshot Analysis		HL, M12
12.	Safety	VF4	Listing of Plasma HIV-1 RNA and CD4+ Cell Count for subjects with Confirmed Virologic Failure		M12, EOS
Exposure and Treatment Compliance					
13.	Safety	207966/primary_15/L12	Listing of Exposure Data	ICH E3 Remove Phase Day	M12
Adverse Events					
14.	Safety	AE8	Listing of All Adverse Events	ICH E3 Add column for Phase, Visit, and Implementation arm; see gsk1265744/mid207966/primary_15/L19	HL, M12
15.	Safety	AE8	Listing of Grade 3-5 Adverse Events	Add column for Phase, Visit, and Implementation arm; see gsk1265744/mid207966/primary_15/L19	M12
16.	Safety	AE7	Listing of Subject Numbers for Individual Adverse Events	ICH E3	M12
17.	Safety	201584/primary_07/L22	Listing of Changes in Intensity/Grades of Study Drug Injection Site Adverse Events	Remove phase treatment, add visit	M12, EOS

ICH: Listings					
No.	Population	GSK Standard / Example Shell	Title	Programming Notes	Deliverable
18.	Safety	AE8	Listing of COVID-19 Adverse Events	Add column for Phase, Visit, and Implementation arm; see gsk1265744/mid207966/primary_15/L19 Include Y/N column checked if the AE lead to discontinuation	HL, M12
19.	Safety	PAN12	Listing of COVID-19 Assessments and Symptom Assessments	Add column for Phase and Visit	M12
20.	Safety	PAN5	Country Level Listing of Start Dates of COVID-19 Pandemic Measures		M12, EOS
Serious and Other Significant Adverse Events					
21.	Safety	AE8	Listing of Fatal Serious Adverse Events	ICH E3 Add column for Phase, Visit, and Implementation arm	M12
22.	Safety	AE8	Listing of Non-Fatal Serious Adverse Events	ICH E3 Add column for Phase, Visit, and Implementation arm	M12, EOS
23.	Safety	AE8	Listing of Adverse Events Leading to Withdrawal from Study / Permanent Discontinuation of Study Treatment	ICH E3 Add column for Phase, Visit, and Implementation arm	M12, EOS
Laboratory					
24.	Safety	LB14	Listing of Laboratory Data with Character Results	ICH E3 Add Category, Phase/Period, Visit	M12

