3. PLANNED ANALYSES

This RAP describes standard analyses that will be applied to descriptively summarize clinical adverse events, laboratory evaluations, virologic parameters and other clinical safety and efficacy outcomes.

Details pertaining to reporting of survey/interview data and health outcomes/effectiveness analyses will be described in a separate analysis plan provided by Evidera or other CRO partner under GSK's oversight.

At least three analyses will be conducted to evaluate primary and secondary objectives of the protocol; an interim analysis after 50% of subjects have received their 3rd injection, and interim analysis after 100% of subjects have received their 3rd injection, and finally the primary analysis at Month 12. Further data cuts and analyses may be conducted as necessary, in order to support for internal use and publications.

A final end-of-study (EOS) analysis will be conducted when all subjects have completed the study.

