3.2. Final Analyses

The planned Month 12 primary analysis will be performed after the completion of the following sequential steps:

- All participants have completed Month 12 of the study as defined in the protocol, including any required re-tests.
- All required database cleaning activities have been completed and final database release (DBR) and database freeze (DBF) has been declared by Data Management.

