8. SAFETY ANALYSES

The safety analyses will be based on the Safety and Long Term Follow-up (LTFU) populations, unless otherwise specified.

For the interim analyses, adherence to dosing will be reported for the Safety population. For the Month 12 primary analysis, outputs will be presented for the Safety population in the Intervention Phase unless otherwise specified. For the EOS analysis, outputs will be presented for the Safety population in the Intervention and Extension phases as well as for the LTFU population in the LTFU phase.

For the Month 12 analysis, a set of separate outputs will also be presented for the oral lead-in period, including a summary of adverse events, SAEs, AEs leading to withdrawal, post-baseline emergent chemistry/haematology abnormalities, and subjects with hepatobiliary abnormality criteria.

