13.12. Appendix 12: List of Data Displays

All data displays will use the term “subject” rather than “participant” in accordance with CDSIC and GSK Statistical Display Standards.

Where applicable, all summary displays will present data across both the Intervention and Extension phases unless explicitly stated otherwise in the display title.

At EOS, the RAPIDO Data Viewer will be produced to allow for the clinical team to review ADaM data directly related to adverse events, exposure, HIV-1 RNA, and labs. This will take the place of some, previously standard generic listings from these categories. Listings including results of pregnancy details will only be included if a pregnancy occurs.

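### Fatal SAEs are listed only at Month 12 while non-fatal SAEs are listed again at end of study, so a death after the Month 12 cut is in neither SAE listing of the final report

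*SAP*

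**What the plan says.** SAP 13.12.10 includes Listing 21, "Listing of Fatal Serious Adverse Events". With its programming note and deliverable the row reads "Listing of Fatal Serious Adverse Events ICH E3 Add column for Phase, Visit, and Implementation arm M12", and the row for Listing 22 reads "Listing of Non-Fatal Serious Adverse Events ICH E3 Add column for Phase, Visit, and Implementation arm M12, EOS". Listing 23, on events leading to study withdrawal or permanent treatment discontinuation, is also due at Month 12 and EOS.

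On timing, SAP 3.2 makes the Month 12 analysis wait until "All participants have completed Month 12 of the study as defined in the protocol, including any required re-tests". SAP section 3 adds: "A final end-of-study (EOS) analysis will be conducted when all subjects have completed the study".

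On scope, SAP section 8 says: "For the EOS analysis, outputs will be presented for the Safety population in the Intervention and Extension phases", and the same sentence adds the LTFU population in the LTFU phase.

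SAP 13.12 introduces the RAPIDO Data Viewer at EOS so that the clinical team can review adverse event, exposure, HIV-1 RNA and laboratory data. Of the displays it affects, the SAP says only: "This will take the place of some, previously standard generic listings from these categories". It does not name them.

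**The concern.** At EOS the plan lists serious events that were survived and omits those that were not. Listing 22 excludes deaths by its title, and the listing that would show them is not rerun. Yet the EOS report is meant to cover phases that can run well past the Month 12 cut. Under Protocol 6.8, Extension dosing continues until marketed product is available or another stopping condition is met. Under Protocol 4.3.4, LTFU lasts 52 weeks from the last injection.

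At stake is the line-by-line record of the gravest safety outcome in the final report: which event, on what date, judged related or not, and in which implementation arm. The trial collects this detail. Protocol 8.5.6 requires a dedicated death form, and Protocol 8.5.7 requires prompt reporting of any death.

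**Working it through.** No figure in the plan needs to be reproduced. The check compares the deliverable column of the SAP's display list across every listing that could carry a fatal event.

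**Step 1. Listings in SAP 13.12.10 and 13.12.11.**

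| Listing | Content | Deliverable | Carries a death after the Month 12 cut? |
|---|---|---|---|
| 21 | Fatal SAEs | M12 | No, not rerun |
| 22 | Non-fatal SAEs | M12, EOS | No, excluded by title |
| 23 | AEs leading to withdrawal or discontinuation | M12, EOS | Only if recorded as such |
| 14 | All AEs | HL, M12 | No |
| 15 | Grade 3-5 AEs | M12 | No |
| 16 | Subject numbers for individual AEs | M12 | No |
| 18 | COVID-19 AEs | HL, M12 | No |
| 54 | AEs in pregnant participants | EOS | Only for that subgroup |
| 1 | Reasons for study withdrawal | M12, EOS | As a disposition reason, not an event record |

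Listings 21, 22 and 23 share the AE8 shell, the Safety population, the ICH E3 tag and the added columns for phase, visit and implementation arm. They differ only in title and, for Listing 21, in deliverable.

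**Step 2. When the gap opens.** The Month 12 cut comes after the last participant has completed Month 12. By then, earlier enrollees may already be in Extension or LTFU. A death among them before the cut is in the Month 12 run of Listing 21, which has a phase column. Only deaths after the cut are affected.

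**Step 3. What the EOS tables still give** (SAP 13.12.7; all have EOS as a deliverable).

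- Table 3.9: count of fatal AEs by study phase.
- Tables 3.27 and 3.29 (LTFU): SAEs by organ class and maximum grade. Protocol 10.2 grades AE-related deaths as 5, so they appear at that grade.
- Table 3.30: SAEs by preferred term.
- Table 3.31: SAEs by visit and maximum severity.
- Tables 3.19 and 3.21 (LTFU): drug-related AEs by organ class and maximum grade.

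**Step 4. What remains missing.** These are separate aggregate tables. None of them ties event, date, relatedness and implementation arm to one participant. For a death after the cut, only Listing 23 could do so, and only if the event was recorded as leading to withdrawal or discontinuation.

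**The case against.** The strongest reply is that Listing 21 was dropped on purpose. SAP 1.1 records that EOS display status was revised with the Data Viewer in mind. SAP 13.12 names adverse events among the data it covers, and Listings 14, 15 and 18, on the same shell, also lack an EOS delivery. That may be the reason. But the viewer is described as a review tool for the clinical team, the replaced listings are not named, and the rationale does not explain why the non-fatal listing was kept. If the omission was intended, the SAP should say where fatal SAEs are listed at EOS.

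A second reply is that Listing 23 covers withdrawal from the study as well as treatment discontinuation, so a death in LTFU could enter it. Table 3.34 plans that category for the LTFU population, and the Snapshot rules in SAP Appendix 8 treat death as a withdrawal reason taken from the conclusion form. This stands as a possible route but not an assured one, because it depends on how the event is recorded.

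A third reply is that the aggregate tables already show phase, cause, visit and relatedness. This stands, and it limits the point to the individual record.

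**Conclusion.** The mismatch is real and narrow. A fatal SAE after the Month 12 cut falls outside both SAE listings at EOS, and its only participant-level AE line is a conditional one in Listing 23 (or Listing 54, for a pregnant participant). No primary conclusion is affected.

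Four stronger readings are tempting, and the documents do not support them.

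- A reader might infer that late deaths are missing from the final report. They are counted and classified in the EOS tables.
- A reader might infer that no such death can be listed. Listing 23 can carry one, and Listing 1 can show it as a withdrawal reason.
- A reader might infer that every Extension or LTFU death is affected, or that most safety follow-up lies after the cut. Deaths before the cut are listed at Month 12. The plan gives no figure for the share of follow-up beyond it, and once marketed product is locally available only safety-related discontinuations must enter LTFU (Protocol 4.3.4).
- A reader might infer that Listing 15 must also be rerun. That is a preference: it is a general AE listing of the kind the SAP says the viewer may replace.

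The conclusion rests on two assumptions: that the deliverable column means what it says, and that the AE8 shell, which the SAP does not reproduce, is the usual one-line-per-event listing with dates and relatedness. There may be few such deaths or none. The display should still be specified in advance.

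**What to change.** In SAP 13.12.10, change the deliverable of Listing 21 from M12 to M12, EOS, and state that the EOS run covers the Intervention, Extension and LTFU phases. The cost is one table cell and a rerun of a program that will already exist for Month 12. No new data are needed.

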13.12.11. Non-ICH Listings

Non-ICH: Listings					
No.	Population	GSK Standard GSK Statistical Display Standard / Example Shell	Title	Programming Notes	Deliverable
Subject Disposition					
25.	Screened	ES7	Listing of Reasons for Screen Failure	Journal Guidelines	M12
26.	Screened	ES9	Listing of Subjects Who Were Rescreened		M12
27.	Enrolled	SD2	Listing of Reasons for Study Treatment Discontinuation During the Oral Lead-in Period	Add column for Visit and Implementation arm	M12
28.	Safety	TA1	Listing of Planned and Actual Treatments by Implementation Arm	GSK Statistical Display Standard	M12
29.	Safety	TA1	Listing of Subjects with Missed Visits Due to Covid-19 by Implementation Arm	Add a column indicating whether a remote visit was performed (Y/N)	M12, EOS
Prior and Concomitant Medications					
30.	Safety	207966/primary_15/Listing 36	Listing of Prior ART Medications	Remove the column 'Phase during Which Concomitant'	M12
31.	Safety	207966/primary_15/Listing 37	Listing of Concomitant ART Medications	Add column for Phase, Visit, and Implementation arm Add a column specifying "SOC Oral Bridging?" which has values of "Yes" and "No".	HL, M12, EOS
32.	Safety	207966/primary_15/Listing 38	Listing of ART Medications Received during Long-term Follow-up Phase	Remove the column 'Phase during Which Concomitant'	M12, EOS
Medical History					
33.	Safety	201584/primary_01/L43	Listing of Medical History of Seizure		M12

CONFIDENTIAL

213199

Efficacy					
34.	Safety	CDC4	Listing of CDC Classification of HIV-1 Infection at Baseline		M12
35.	Safety	CDC5	Listing of CDC Stage 3 HIV-1 Associated Conditions	Add column for Phase, Visit	M12, EOS
Exposure					
36.	Safety	EX3	Listing of Actual Visit Dates and Day Since Last Dose	Add column for implementation arm	IA1, IA2, M12, EOS
37.	Safety	207966/primary_15/L60	Listing of Oral Bridging Exposure Data	Add visit to phase. Add column for implementation arm and to identify COVID relatedness.	HL, M12, EOS
38.	Safety	207966/primary_15/L60	Listing of Exposure Data for Subjects Who Received Oral Bridging	Add visit to phase. Add columns for implementation arm, Total Volume Injected / Duration of Oral Treatment	M12
Hepatobiliary (Liver)					
39.	Safety	LIVER5	Listing of Liver Monitoring/Stopping Event Reporting	GSK Statistical Display Standard Add column for Phase, Visit	M12, EOS
40.	Safety	LIVER15	Liver Stopping Event Profile	GSK Statistical Display Standard Add column for Phase, Visit	M12, EOS
41.	Safety	LIVER13	Listing of Subjects Meeting Hepatobiliary Laboratory Criteria Post-Baseline	GSK Statistical Display Standard Add column for Phase, Visit	HL, M12, EOS
42.	Safety	LB12	Listing of ALT, AST, Bilirubin (including Total and Direct Bilirubin), INR, and ALP for Subjects Meeting Hepatobiliary Lab Abnormality Criteria	Add column for Phase, Visit	M12, EOS

CONFIDENTIAL

213199

Other					
43.	Safety	EG3	Listing of All ECG Values for Subjects with Recorded ECG Data	GSK Statistical Display Standard Add column for Phase, Visit	M12
44.	Safety	PREG1	Listing of Subjects Who Became Pregnant During the Study	GSK Statistical Display Standard Add column for Phase, Visit	M12, EOS
45.	Safety	201584/primary_17/L54	Listing of Replication Capacity in IN and PR/RT Region	Add column for Phase, Visit	M12, EOS
Vital Signs					
46.	Safety	VS5	Listing of Vital Sign Results	GSK Statistical Display Standard Required for ClinPharm studies only.	M12
Pharmacokinetic					
47.	Safety	PK07	Listing of Plasma CAB Pharmacokinetic Concentration-Time Data		M12, EOS
48.	Safety	PK07	Listing of Plasma RPV Pharmacokinetic Concentration-Time Data		M12, EOS
Pregnancy (conditional on incidence of pregnancy)					
49.	Safety	PREG_01	Listing of Pregnancy Details and Outcomes	Results to be pulled from the Pregnancy Notification Form	EOS
50.	Safety	PREG_02	Listing of Pregnancy Outcomes	Results to be pulled from the Pregnancy Follow-up Form	EOS
51.	Safety	207966/primary_15/Listing 37	Listing of Concomitant Medications for Pregnant Participants During and After Pregnancy	Results should reconcile with the Pregnancy Notification and Follow-up Forms Follow specifications for the current Listing 31	EOS
52.	Safety	SNAPSHOT11	Listing of Qualitative and Quantitative Plasma HIV-1 RNA Data for Pregnant Participants	Follow specifications for the current Listing 10	EOS
53.	Safety	207966/primary_15/L12	Listing of Exposure Data for Pregnant Participants	Follow specifications for the current Listing 13	EOS

CONFIDENTIAL

213199

54.	Safety	AE8	Listing of Adverse Events for Pregnant Participants During and After Pregnancy	Follow specifications for the current Listing 14	EOS
55.	Safety	LB5A	Listing of All Laboratory Data for Pregnant Participants During and After Pregnancy		EOS
56.	Safety	PK07	Listing of Plasma CAB Pharmacokinetic Concentration-Time Data for Pregnant Participants During and After Pregnancy	Follow specifications for the current Listing 43	EOS
57.	Safety	PK07	Listing of Plasma RPV Pharmacokinetic Concentration-Time Data for Pregnant Participants During and After Pregnancy	Follow specifications for the current Listing 44	EOS

13.13. Appendix 13: Example Mock Shells for Data Displays

Protocol: 213199
 Population: Safety

Page 1 of x

Table DISP_T1
 Summary of Subject Disposition at Each Study Phase

Study Phase		CAB Oral + RPV Oral (N=100)	CAB LA + RPV LA (N=100)	Total (N=200)
Intervention Phase	ENTERED	xx (xx.x%)	xx (xx.x%)	xx (xx.x%)
	COMPLETED	xx (xx.x%)	xx (xx.x%)	xx (xx.x%)
	WITHDRAWN	xx (xx.x%)	xx (xx.x%)	xx (xx.x%)
	COVID-19 RELATED	xx (xx.x%)	xx (xx.x%)	xx (xx.x%)
Completed Intervention Phase but Withdrew Prior to Extension Phase	ENTERED			xx (xx.x%)
	COMPLETED			xx (xx.x%)
	WITHDRAWN			xx (xx.x%)
	COVID-19 RELATED			xx (xx.x%)
Extension Phase	ENTERED			xx (xx.x%)
	COMPLETED			xx (xx.x%)
	WITHDRAWN			xx (xx.x%)
	COVID-19 RELATED			xx (xx.x%)
Long-term Follow-up Phase	ENTERED			xx (xx.x%)
	COMPLETED			xx (xx.x%)
	WITHDRAWN			xx (xx.x%)
	COVID-19 RELATED			xx (xx.x%)

CONFIDENTIAL

213199

Intervention/Extension phase status and reason for withdrawal is based on date and reason collected in the study treatment discontinuation form.

A subject is considered to have entered the Extension phase if the subject received a Month 14 injection or had any assessments collected at any Extension phase nominal visit.

A subject is considered to have entered the Long-term Follow-up phase if they have received at least one CAB and/or RPV injection and have started Long-term Follow-up ART

Long-term Follow-up completion/withdrawal is based on data collected in the Study Conclusion form.

PPD [REDACTED] /arenv/arprod/gsk1265744/mid209493/primary_01/drivers/t_sp_sd_phase.sas 02FEB2021 11:58

Protocol: 213199
Page 1 of x

Population: Safety

Table DISP_T2
Summary of Reasons for Withdrawal at Each Study Phase

Phase	Primary Reason[1]/Subreason[2] for Withdrawal	CAB Oral + RPV Oral (N=100)	CAB LA + RPV LA (N=100)	Total (N=200)
Intervention Phase	ADVERSE EVENT	xx (xx.x%)	xx (xx.x%)	xx (xx.x%)
	COVID-19 RELATED	x (xx.x%)	x (xx.x%)	x (xx.x%)
	LACK OF EFFICACY	xx (xx.x%)	xx (xx.x%)	xx (xx.x%)
	PROTOCOL DEVIATION	xx (xx.x%)	xx (xx.x%)	xx (xx.x%)
	COVID-19 RELATED	x (xx.x%)	x (xx.x%)	x (xx.x%)
	PROHIBITED MEDICATION USE	x (xx.x%)	x (xx.x%)	x (xx.x%)
	NON-COMPLIANCE WITH STUDY TREATMENT	x (xx.x%)	x (xx.x%)	x (xx.x%)
	SUBJECT REACHED PROTOCOL-DEFINED STOPPING CRITERIA	xx (xx.x%)	xx (xx.x%)	xx (xx.x%)
	STUDY TERMINATED BY SPONSOR	xx (xx.x%)	xx (xx.x%)	xx (xx.x%)
	LOST TO FOLLOW-UP	xx (xx.x%)	xx (xx.x%)	xx (xx.x%)
	INVESTIGATOR SITE CLOSED	xx (xx.x%)	xx (xx.x%)	xx (xx.x%)
	PHYSICIAN DECISION	xx (xx.x%)	xx (xx.x%)	xx (xx.x%)
	WITHDRAWAL BY SUBJECT	xx (xx.x%)	xx (xx.x%)	xx (xx.x%)
	COVID-19 RELATED	x (xx.x%)	x (xx.x%)	x (xx.x%)
	FREQUENCY OF INJECTIONS	x (xx.x%)	x (xx.x%)	x (xx.x%)
Long-term Follow-up Phase	LOST TO FOLLOW-UP			xx (xx.x%)
	WITHDRAWAL BY SUBJECT			xx (xx.x%)
	SUBJECT RELOCATED			x (xx.x%)

CONFIDENTIAL

213199

BURDEN OF PROCEDURES

x (xx.x%)

[1] Subjects may have only one primary reason.

[2] Percentages for subreasons may sum to more or less than 100%. Subjects may have more than one subreason underneath a single primary reason. Subjects are not required to indicate subreasons.

Intervention/Extension phase: status and reason for withdrawal based on date and reason collected in the study treatment discontinuation form. Long term Follow-up: completion/withdrawal based on data collected in the Study Conclusion form.

Protocol: 213199
 Population: Safety

Page 1 of 1

Table EFF_T1
 Summary of Study Outcomes (50 c/mL cutoff) at Month 12 (Intervention Phase)
 - Snapshot Analysis

Outcome	Q4W IM (N=xx)
HIV-1 RNA<50 c/mL	xx (xx%)
HIV-1 RNA>=50 c/mL	xx (xx%)
Data in window not below threshold	xx (xx%)
Discontinued for lack of efficacy	xx (xx%)
Discontinued for other reason while not below threshold	xx (xx%)
Change in ART [1]	xx (xx%)
No Virologic Data	xx (xx%)
Discontinued study due to AE or Death	xx (xx%)
Discontinued study for Other Reasons	xx (xx%)
On study but missing data in window	xx (xx%)

[1] Excludes CAB + RPV Oral Bridging and COVID-19 related temporary oral bridging with SOC.

Protocol: mid213199
 Population: Safety

Page 1 of 1

Table EFF_T2
 Summary of Study Outcomes (50 c/mL cutoff) at Month 12 (Intervention Phase)
 - Snapshot Analysis

Outcome	Q4W IM (N=xx)
HIV-1 RNA<50 c/mL	xx (xx%)
HIV-1 RNA≥50 c/mL	xx (xx%)
Data in window not below threshold	xx (xx%)
Non-COVID-19 related	xx (xx%)
Discontinued for lack of efficacy	xx (xx%)
Discontinued for other reason while not below threshold	xx (xx%)
COVID-19 related	xx (xx%)
Discontinued for lack of efficacy	xx (xx%)
Discontinued for other reason while not below threshold	xx (xx%)
Change in ART [1]	xx (xx%)
No Virologic Data	xx (xx%)
Non-COVID-19 related	xx (xx%)
Discontinued study due to AE or Death	xx (xx%)
Discontinued study for Other Reasons	xx (xx%)
On study but missing data in window	xx (xx%)
COVID-19 related	xx (xx%)
Discontinued study due to AE or Death	xx (xx%)
Discontinued study for Other Reasons	xx (xx%)
On study but missing data in window	xx (xx%)

[1] Excludes CAB + RPV Oral Bridging and COVID-19 related temporary oral bridging with SOC.

Protocol: mid213199
 Population: Safety

Table SAF_T1

Summary of Adherence to CAB LA + RPV LA Dosing Schedule by Visit, Country, Site, and COVID Impacted/Non-Impacted (Intervention Phase)

Country: xxxxx {Programmer's Note: repeat for each of 5 countries overall, each individual site, and total}
 Site ID: xxxxx
 COVID-19: xxx {non-impacted + impacted/non-impacted/impacted}

Timeliness of Injections Relative to Date of Projected Dosing Visits	Month 2	Month 4	Month 6	Month 8	Month 10	Month 12	Total
No. of Expected Injection Visits	xxxx	xxxx	xxxx	xxxx	xxxx	xxxx	xxxx
<-14 days	xx (%)	xx (%)	xx (%)				
-14 days to - 8 days	xx (%)	xx (%)	xx (%)				
-7 days to - 1 days	xx (%)	xx (%)	xx (%)				
0	xx (%)	xx (%)	xx (%)				
1 days to 7 days	xx (%)	xx (%)	xx (%)				
8 days to 14 days	xx (%)	xx (%)	xx (%)				
> 14 days	xx (%)	xx (%)	xx (%)				
Missed Injection without OB (non-COVID-19 related)	xx (%)	xx (%)	xx (%)				
Missed Injection without OB (COVID-1 related)	xx (%)	xx (%)	xx (%)				
Missed Injection with OB (non-COVID-19 related)	xx (%)	xx (%)	xx (%)				
Missed Injection with OB (COVID-19 related)	xx (%)	xx (%)	xx (%)				
Late Out of Window Injections (days outside +7 day window)							
n	xxx	xxx	xxx	xxx	xxx	xxx	xxx
Mean	xxx.x	xxx.x	xxx.x	xxx.x	xxx.x	xxx.x	xxx.x
SD	xxx.xx	xxx.xx	xxx.xx	xxx.xx	xxx.xx	xxx.xx	xxx.xx
Median	xxx.x	xxx.x	xxx.x	xxx.x	xxx.x	xxx.x	xxx.x
Q1	xxx	xxx	xxx	xxx	xxx	xxx	xxx
Q3	xxx	xxx	xxx	xxx	xxx	xxx	xxx
Min	xxx	xxx	xxx	xxx	xxx	xxx	xxx

CONFIDENTIAL

213199

Timeliness of Injections Relative to Date of Projected Dosing Visits	Month 2	Month 4	Month 6	Month 8	Month 10	Month 12	Total
Max	xxx	xxx	xxx	xxx	xxx	xxx	xxx

CONFIDENTIAL

213199

Protocol: mid213199
Population: Safety

Page 1 of 1

Table SAF_T2

Summary of Adherence to CAB LA + RPV LA Dosing Schedule by Visit, Subgroup, and COVID Impacted/Non-Impacted (Intervention Phase)

Subgroup: xxxx {Programmer's Note: repeat for each subgroup}

COVID-19: xxx {Programmer's Note: repeat for non-impacted + impacted/non-impacted/impacted}

Timeliness of Injections Relative to Date of Projected Dosing Visits	Month 2	Month 4	Month 6	Month 8	Month 10	Month 12	Total
No. of Expected Injection Visits	xxxx	xxxx	xxxx	xxxx	xxxx	xxxx	xxxx
<-14 days	xx (%)	xx (%)	xx (%)				
-14 days to - 8 days	xx (%)	xx (%)	xx (%)				
-7 days to - 1 days	xx (%)	xx (%)	xx (%)				
0	xx (%)	xx (%)	xx (%)				
1 days to 7 days	xx (%)	xx (%)	xx (%)				
8 days to 14 days	xx (%)	xx (%)	xx (%)				
> 14 days	xx (%)	xx (%)	xx (%)				
Missed Injection without OB (non-COVID-19 related)	xx (%)	xx (%)	xx (%)				
Missed Injection without OB (COVID-1 related)	xx (%)	xx (%)	xx (%)				
Missed Injection with OB (non-COVID-19 related)	xx (%)	xx (%)	xx (%)				
Missed Injection with OB (COVID-19 related)	xx (%)	xx (%)	xx (%)				
Late Out of Window Injections (days outside +7 day window)							
n	xxx	xxx	xxx	xxx	xxx	xxx	xxx
Mean	xxx.x	xxx.x	xxx.x	xxx.x	xxx.x	xxx.x	xxx.x
SD	xxx.xx	xxx.xx	xxx.xx	xxx.xx	xxx.xx	xxx.xx	xxx.xx
Median	xxx.x	xxx.x	xxx.x	xxx.x	xxx.x	xxx.x	xxx.x
Q1	xxx	xxx	xxx	xxx	xxx	xxx	xxx
Q3	xxx	xxx	xxx	xxx	xxx	xxx	xxx
Min	xxx	xxx	xxx	xxx	xxx	xxx	xxx

CONFIDENTIAL

213199

Timeliness of Injections Relative to Date of Projected Dosing Visits	Month 2	Month 4	Month 6	Month 8	Month 10	Month 12	Total
Max	xxx	xxx	xxx	xxx	xxx	xxx	xxx

Protocol: mid213199

Page 1 of 1

Population: Safety

Table OTR_T1
Summary of Study Visit Length (minutes) by Visit, Country, and Site

Country Site	N			Month 1	Month 2	Month 6	Month 8	Total
Overall Overall		Lead Time	n	xxx	xxx	xxx	xxx	xxx
			Mean	xx.x	xx.xx	xx.x	xx.x	xx.x
			SD	xx.xx	xx.xx	xx.xx	xx.xx	xx.xx
			Median	xx.x	xx.x	xx.x	xx.x	xx.x
			Q1	xx.x	xx.x	xx.x	xx.x	xx.x
			Q3	xx.x	xx.x	xx.x	xx.x	xx.x
			Min.	xx	xx	xx	xx	xx
			Max.	xx	xx	xx	xx	xx
		Process Time	n	xxx	xxx	xxx	xxx	xxx
			Mean	xx.x	xx.xx	xx.x	xx.x	xx.x
			SD	xx.xx	xx.xx	xx.xx	xx.xx	xx.xx
			Median	xx.x	xx.x	xx.x	xx.x	xx.x
			Q1	xx.x	xx.x	xx.x	xx.x	xx.x
			Q3	xx.x	xx.x	xx.x	xx.x	xx.x
			Min.	xx	xx	xx	xx	xx
			Max.	xx	xx	xx	xx	xx
		Total Time	n	xxx	xxx	xxx	xxx	xxx
			Mean	xx.x	xx.xx	xx.x	xx.x	xx.x
			SD	xx.xx	xx.xx	xx.xx	xx.xx	xx.xx
			Median	xx.x	xx.x	xx.x	xx.x	xx.x
			Etc.	xx.x	xx.x	xx.x	xx.x	xx.x

Lead Time = Actual Start Time of Appointment - Arrival Time.

CONFIDENTIAL

213199

Process Time = Actual End Time of Appointment - Actual Start Time of Appointment.
[Programmers Note: repeat for each, country site, and total]

Protocol: mid213199
 Population: Safety

Table OTR_T2
 Summary of Study Visit Length (minutes) by Visit and Subgroup

Subgroup Strata	N			Month 1	Month 2	Month 6	Month 8	Total
Sex Male		Lead Time	n	xxx	xxx	xxx	xxx	xxx
			Mean	xx.x	xx.xx	xx.x	xx.x	xx.x
			SD	xx.xx	xx.xx	xx.xx	xx.xx	xx.xx
			Median	xx.x	xx.x	xx.x	xx.x	xx.x
			Q1	xx.x	xx.x	xx.x	xx.x	xx.x
			Q3	xx.x	xx.x	xx.x	xx.x	xx.x
			Min.	xx	xx	xx	xx	xx
			Max.	xx	xx	xx	xx	xx
		Process Time	n	xxx	xxx	xxx	xxx	xxx
			Mean	xx.x	xx.xx	xx.x	xx.x	xx.x
			SD	xx.xx	xx.xx	xx.xx	xx.xx	xx.xx
			Median	xx.x	xx.x	xx.x	xx.x	xx.x
			Q1	xx.x	xx.x	xx.x	xx.x	xx.x
			Q3	xx.x	xx.x	xx.x	xx.x	xx.x
			Min.	xx	xx	xx	xx	xx
			Max.	xx	xx	xx	xx	xx
		Total Time	n	xxx	xxx	xxx	xxx	xxx
			Mean	xx.x	xx.xx	xx.x	xx.x	xx.x
			SD	xx.xx	xx.xx	xx.xx	xx.xx	xx.xx
			Median	xx.x	xx.x	xx.x	xx.x	xx.x
			Etc.	xx.x	xx.x	xx.x	xx.x	xx.x

Lead Time = Actual Start Time of Appointment - Arrival Time.

Process Time = Actual End Time of Appointment - Actual Start Time of Appointment.

[Programmers Note: repeat for each Subgroup and Strata]

CONFIDENTIAL

213199

Preg_01

Protocol: 213199						Page 1 of x		
Population: Safety						Listing 49 (Data as of: 30MAY2011)		
Listing of Pregnancy Details								
Site Id.: PPD								
Unique Subject Id./ Subject Id./Implementation Arm	Mother's Year of Birth	Date of Last Menstrual Period/ Study Day	Estimated Date of Delivery/ Study Day	Contraception?/Contraception Type/Conception Type (Normal, IVF) [1]	Relevant Lab Tests and Procedures	No. of Previous Pregnancies		Additional Factors that May Impact Pregnancy
						Pre-term	Full-term	
PPD /CAB LA + RPV LA ARM-e	xxxx	2012-PPD T23:59/1	2012-PPD T23:59/1	Y/Birth Control/Normal	Amniocenteses performed	Spontaneous Abortion (n): x	Normal Births (n): x	
						Elective Abortion (n): x	Stillbirths (n): x	
						Other (n): x	Born w/Defects (n): x	
PPD /CAB LA + RPV LA ARM-e	xxxx	2012-PPD T23:59/1	2012-PPD T23:59/1	N/ /Normal		Spontaneous Abortion (n): x	Normal Births (n): x	
						Elective Abortion (n): x	Stillbirths (n): x	
						Other (n): x	Born w/Defects (n): x	

[1] Normal conception includes the use of fertility drugs. IVF = in vitro fertilization.

CONFIDENTIAL

213199

Preg_02

Protocol: 213199								Page 1 of x
Population: Safety		Listing 50						(Data as of: 30MAY2011)
		Listing of Pregnancy Outcomes						
Site Id.: PPD								
Unique Subject Id./ Subject Id./Implementation Arm	Pregnancy Status [1]	Foetal/Neonatal Status (Normal, Birth Defect, Other)	Origin of Birth Defect Known?	Date of Birth, miscarriage, termination / Study Day / Gestational Weeks	Infant Sex/Length (cm)/Weight (g)	Apgar Score (0-10) 1st / 2nd	Pregnancy Duration (days) [2]	Additional Pregnancy Details
PPD /CAB LA + RPV LA ARM-e	Delivery: Normal	Birth Defect	Yes : xxxx	2012-PPD T23:59/ 1 / 38	M / 50 / 2500	8/8	xx	
PPD CAB LA + RPV LA ARM-e	PPD	NA	NA	2012-PPD T23:59/ 1 / 36	NA	0	xx	SAE delivery complication

